## 8.1 Provider-directed Interventions

**Provider Training:** Multifaceted approach to education of providers with direct care responsibilities for patients with advanced dementia. Training initiatives focus on appropriate diagnosis and treatment of suspected UTIs and LRIs in patients with advanced dementia. All training initiatives include application of recommended diagnostic criteria, inclusion of goals of care in development of treatment plan, and provider communication training to optimize communication with healthcare proxies throughout the process. Communication training provided in the seminar and online course is further reinforced with provision of a communication tips pocket card.

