### **9.2 Resident assessments**

Resident data will be collected by RAs masked to the study arms. All data will be obtained from the residents' charts except for functional status and proxy ability to communicate in English, which will be ascertained in a 1-minute nurse interview. Data is collected from the medical records of enrolled residents every 2 months for up to 12 months, unless the resident passes or the proxy requests to opt out during that time. Their charts are abstracted at baseline, q2months, and within 30 days of death to determine whether antimicrobials were prescribed. If a treated episode was a suspected LRI or UTI, documented signs/symptoms will be ascertained to assess whether minimal criteria to start antimicrobials were present. Procedures used to evaluate these episodes (chest x-rays, bladder catheterization, blood draws, hospital transfer), and documented advance care planning about infection management (provider/proxy discussions and advance directives to withhold antimicrobials) will also be collected. A 1-minute nurse interview at baseline will also be done to assess the resident's functional status.

Demographic: (baseline) age, gender, race, ethnicity, length of NH stay, residing in a special care dementia unit, and proxy contact information (for mailing booklet) and relationship to resident.

Medical co-morbidity: (baseline) All active medical diagnoses.

Functional status: (baseline; nurse) Bedford Alzheimer's Nursing Severity-Subscale (BANS range, 7-28; higher score worse disability)

Antimicrobial exposure: (q2months, death) While analyses focus on treatment of suspected LRIs and UTIs, details about all antimicrobial courses will be ascertained from the medication administration records, including; suspected diagnoses, administration dates, agent, dose, route,

and prescribing provider. There are many ways to quantify antimicrobial exposure. We chose number of courses/person-years as our primary outcome as it best captures the intent of the intervention which is to reduce antimicrobial initiation. A course will be defined as starting an antimicrobial after a > 3-day treatment-free interval. Multiple antimicrobials given simultaneously for an episode will be considered single course for analytic purposes. For descriptive purposes, we will also quantify antimicrobial exposure as days of therapy (DOT)/person-days.

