Treated suspected UTIs and LRIs: (q2months, death): Documented details will be collected for treated suspected UTIs and LRIs, including: i. vital signs, mental status changes, localized signs and symptoms (e.g., lung sounds, cough, hematuria), ii. procedures used to evaluate including bladder catheterizations, chest x-rays, blood draws, iii. hospital transfer (admission or emergency room (ER), and vi. treatment discussions between providers and proxies. Signs and symptoms will be used to determine whether minimal criteria to initiate antimicrobials were met as operationalized in SPREAD and the pilot study.

Advance care planning: (baseline, q2months, death). The occurrence and date of advance care planning events will be ascertained from all available documentation (e.g., progress notes physician orders, POLST forms) and will include: discussions between providers and proxies about infection management and new directives to withhold antimicrobials (intravenous, intramuscular and/or oral) will be ascertained. Do-not-resuscitate and do-not-hospitalize orders will also be collected for descriptive purposes.

Devices: (baseline, q2months, death) feeding tubes, foley catheters

Health services: (q2months, death) hospitalizations, emergency room visits, hospice enrollment. 3.C.vii.1.i.

Other major new acute illnesses: (q2months, death), e.g. fracture, stroke, seizures. Death: RAs will phone the NH (nursing units) q2month.

Death date will be obtained from the chart.

Data Collection Elements and Protocol			
Data Collected	Purpose	From	When
Eligibility Screen			
Age, length of NH stay, available proxy	Eligibility	Chart	Screen
Advanced dementia	Eligibility	Nurse, Chart	Screen
IF ELIGIBLE			
Resident Characteristics			
Demographic, medical comorbidity, functional status	Descriptive	Chart	Baseline
Antimicrobial exposure			
Total courses for LRIs and UTIs 	1 o Outcome (Aim 1)	Chart, MAR 	q2months, death
Total courses for LRIs and UTIs  not meeting minimal criteria	2 o Outcome (Aim 2)	Chart, MAR 	q2months, death
Burdensome procedures to evaluate suspected LRIs and UTIs	2 o Outcome (Aim 3)	Chart	q2months, death
Advance care planning	2 o Outcome (Aim 3)	Chart	Baseline, q2months, death
Devices	Descriptive	Chart	Baseline, q2months, death
Health services utilization, new acute illnesses	Descriptive	Chart	q2months, death

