#### 13.4.2 Resident Data collection forms

The following data collection forms, programed into redcap are used for resident-level data collection:

- Resident eligibility screening
- Baseline resident chart review
- Resident bimonthly chart reviews
- Post Death Chart review
- Infection Screening (occurs at baseline and bimonthly chart reviews)
- UTI and LRI infection modules (used when either UTI or LRI are recorded during an infection screening)

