# Aim 3: Compare: i. advance care planning and ii. use of burdensome procedures (secondary outcomes).

For H3a, the analysis will compare advance care planning for infections over 12 months defined as having no advance directives to withhold antimicrobials and acquiring a new advance directive to withhold antimicrobials by any route (oral, intramuscular, or intravenous) or having a less restrictive directive to withhold antimicrobials and acquiring a more restrictive directive to withhold antimicrobials. Residents with directives restricting all routes of antimicrobial use at baseline will be excluded. Time to the date of the new directive will be compared between arms using Cox proportional hazards regression modeling with a robust variance estimate to account for clustering at the NH level. Residents who die, dropout, or complete the study without these directives will be censored. HRs and 95% CIs will be generated. For H3b, the main analysis will compare the total number of burdensome procedures (bladder catheterizations, blood draws, chest x-rays, and hospital transfers) used to evaluate a suspected UTI or LRI/person-years between arms. The analytic approach will be same as described for H1.

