### 3.6 Approach to Missing Data, Sensitivity Analyses and Exploratory Analyses

All analyses will follow the intention to treat principle. Based on prior studies, we estimate that 40% of residents will die over 12 months and <1% will be lost to follow-up for other reasons. Residents will contribute data to the analyses up until death (post-death chart review). We will compare the characteristics of residents with missing data to those with complete data. As needed, sensitivity analyses will be performed and imputation techniques employed to account for missing data. The effect of imbalances between key resident characteristics on the intervention effect will be examined as sensitivity analyses using the change-in-effect method.

For H1, an exploratory analysis will examine antimicrobial courses prescribed for any reason (i.e., not limited to antimicrobials prescribed for suspected UTIs or LRIs). We will compare the number of antimicrobial courses/person-years between the intervention and control arms.

For H1 and H2, exploratory analyses will examine UTIs and LRIs separately.

For H3a, a sensitivity analysis will be conducted to examine if the potential competing risk of death impacts the estimates of cumulative incidence using the Fine-Gray regression model.

For H3b, in addition to examining the combination of all burdensome procedures, each type of burdensome procedure (bladder catheterizations, blood draws, chest x-rays, and hospital transfers) will be examined separately, using a similar analytic approach, as exploratory analyses.

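### H3b counts only hospital transfers tied to a suspected UTI or LRI, and no by-arm comparison of all-cause transfers is specified to check a fall

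*SAP*

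**What the plan says.** - **Outcome.** SAP 3.5, Aim 3 (H3b), compares total bladder catheterizations, blood draws, chest x-rays and hospital transfers "used to evaluate a suspected UTI or LRI/person-years between arms".
- **Breakdown.** SAP 3.6 adds that "each type of burdensome procedure (bladder catheterizations, blood draws, chest x-rays, and hospital transfers) will be examined separately". This splits the same components, so the UTI/LRI restriction carries over.
- **Abstraction.** Protocol 9.2 introduces treated episodes of suspected LRI or UTI and then says what is recorded: "Procedures used to evaluate these episodes (chest x-rays, bladder catheterization, blood draws, hospital transfer"). Later in the same section: "Documented details will be collected for treated suspected UTIs and LRIs, including" procedures and hospital transfer (admission or ER). Protocol 13.4.2 is less clear, because it lists "UTI and LRI infection modules (used when either UTI or LRI are recorded during an infection screening") and sets no treatment condition.
- **Intervention.** Protocol 8.1: "Training initiatives focus on appropriate diagnosis and treatment of suspected UTIs and LRIs in patients with advanced dementia". Protocol 9.2 gives reduced antimicrobial initiation as the aim, and SAP 1.8 plans for 30% fewer courses.
- **All-cause data.** Protocol 9.2 collects "Health services: (q2months, death) hospitalizations, emergency room visits, hospice enrollment", and also major new acute illnesses. Its data table labels both as descriptive. The SAP text names no comparison of them by arm, and Appendix A has no table for them.
- **H1 by contrast.** SAP 3.6: "an exploratory analysis will examine antimicrobial courses prescribed for any reason", compared between arms.

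**The concern.** Fewer transfers is the favourable direction for H3b. Deterioration that leads to transfer is also a foreseeable harm of starting fewer antimicrobials. Protocol 5.1.3 itself reports that, in an earlier cohort, residents with pneumonia lived longer when treated, although with more discomfort.

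A transfer can leave the H3b count in two ways without being avoided:

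1. The episode is not treated, so under Protocol 9.2 its details are not abstracted.
2. The episode is no longer labelled a UTI or LRI. Only intervention homes receive the diagnostic training (Protocol 8.1) and the feedback on UTI/LRI prescribing (Protocol 8.1.4).

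Both could occur more often in the intervention arm, and both would lower the count there. With only the UTI/LRI-linked count compared, a reader could not tell fewer transfers from transfers that left the count.

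**Working it through.** The plan states no figure to reproduce on this point. The check compares the texts and then gives scale.

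**Texts side by side.** The SAP defines the outcome on suspected episodes. Protocol 9.2 abstracts the components for treated ones. Treatment is decided after randomization and is the event the intervention aims to reduce. Read as written, Protocol 9.2 makes the set of episodes feeding H3b itself an outcome of the intervention. Untreated suspected episodes are not rare: Protocol 5.1 reports that 72% of suspected infections were treated in the investigators' earlier cohort, so 28% were not.

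**Scale in episodes.** Inputs from SAP 1.8: 205 residents per arm, 0.79 person-years each, 1.26 courses per person-year in controls, 30% reduction.

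- Person-years per arm: 205 × 0.79 = 161.95.
- Control courses: 1.26 × 161.95 = 204.1.
- Intervention courses: 1.26 × 0.70 × 161.95 = 142.8.
- Difference: about 61 episodes.

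On the treated-only reading, up to about 61 intervention-arm episodes leave the set from which transfers are abstracted. The documents do not say how many such episodes are followed by a transfer.

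**What treated-only abstraction could do to H3b as a whole.** This illustration assumes that procedures per treated episode stay constant and that procedures in untreated episodes go unrecorded. SAP 1.8 gives a control rate of 3.25 procedures per person-year.

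- Recorded rate after a 30% fall in treated episodes: 3.25 × 0.70 = 2.28.
- Recorded counts per arm: 3.25 × 161.95 = 526 against 368.
- Chance of a significant H3b difference from this alone: Φ(0.975/√(φ × 5.525/142.1) − 1.96). Here 0.975 and 5.525 are the difference and sum of the two rates, 142.1 = 161.95/1.14, and the design effect is 1 + (15 − 1) × 0.01 = 1.14.
- Result: 0.999 at φ = 1 (Poisson), 0.81 at φ = 3 and 0.60 at φ = 5. The values of φ are assumed.

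This shows what the mechanism could produce. It does not estimate actual bias.

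**Precision of an all-cause comparison.** The design effect at the planned average cluster size is 1 + (410/28 − 1) × 0.01 = 1.136, using the ICC from SAP 1.8. The documents give no all-cause transfer rate, so the rates and the negative binomial dispersion k are assumptions.

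CI factor = exp(1.96 × √(1.136 × 2 × (1 + k × rate × 0.79)/events)), where events = rate × 161.95.

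| Assumed rate per person-year | Events per arm | k = 0 (Poisson) | k = 1 | k = 2 |
|---|---|---|---|---|
| 0.3 | 49 | 1.53 | 1.60 | 1.67 |
| 0.5 | 81 | 1.39 | 1.47 | 1.55 |
| 1.0 | 162 | 1.26 | 1.36 | 1.45 |

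At an observed rate ratio of 1.0, the interval would exclude only rises above about 26% to 67%.

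**The case against.** The strongest opposing points, and what remains of each:

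- **The treated-only reading is not settled.** Every definition of the outcome says suspected, never treated. Protocol 13.4.2 opens the infection modules on any recorded UTI or LRI. Protocol 11.1 and SAP 3.3 list suspected infections and their treatment as separate items collected. This stands as an ambiguity. If all suspected episodes are abstracted, the untreated route closes, but the relabelling route stays open.
- **Relabelling is partly checked.** The any-reason analysis for H1 would show UTI/LRI courses falling while total courses did not. That covers treated episodes given another label. It does not cover relabelled episodes that go untreated, and it does not look at transfers.
- **Some of the fall is intended.** Protocol 5.1.4 regards forgoing evaluation as reasonable when comfort is the goal, and H3b is meant to capture that. This is true, and it is why the all-cause result should be read beside H3b and not replace it.
- **Safety is monitored.** The Data Safety Monitor may see outcomes by masked group, deaths are reported to the monitor, unanticipated adverse events are compared between arms, and descriptive data may be tabulated. None of these is a specified comparison of all-cause transfers.
- **The size is unknown and the check imprecise.** Both hold. The 61 episodes restate the planned H1 effect in courses, and 25 of the 30 percentage points come from courses failing minimal criteria, where evidence of bacterial infection is weakest. An imprecise ratio near 1 would narrow the interpretation without settling it.

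**Conclusion.** The concern holds. H3b and its breakdown by type count transfers only when linked to a suspected UTI or LRI. Protocol 9.2 ties their abstraction to treatment, which the intervention aims to reduce, and no by-arm comparison of the all-cause data is specified.

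The direct consequence is limited to the transfer component, one of four in a secondary outcome. The treated-only rule, if applied, would reach the other three as well. The primary conclusion is unaffected. The size of any distortion cannot be derived from the documents, and the figure of about 61 episodes rests on the treated-only reading and the planned 30% reduction. The point is worth considering, with medium confidence, mainly because the abstraction rule is ambiguous.

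**What to change.** In SAP 3.6, under H3b:

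1. Prespecify an exploratory safety and robustness comparison of all-cause hospital transfers (hospital admissions plus ER visits, any reason) per person-year by arm in the ITT population. Use a count model that allows overdispersion, with follow-up time as offset and variance clustered by nursing home.
2. Report the rate ratio and 95% CI next to the H3b transfer result. Interpret the two estimates together, with no pass/fail rule.
3. Tabulate major new acute illnesses by arm.
4. State whether H3b procedures are abstracted for all suspected UTI/LRI episodes or only for treated ones.

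The cost is one paragraph of wording, one model and one table, from data already abstracted. The downsides are that unrelated causes dilute the infection signal, a moderate rise could not be excluded, and x-rays, blood draws and catheterizations that leave the count stay unchecked.

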### 3.6 Approach to Missing Data, Sensitivity Analyses and Exploratory Analyses

All analyses will follow the intention to treat principle. Based on prior studies, we estimate that 40% of residents will die over 12 months and <1% will be lost to follow-up for other reasons. Residents will contribute data to the analyses up until death (post-death chart review). We will compare the characteristics of residents with missing data to those with complete data. As needed, sensitivity analyses will be performed and imputation techniques employed to account for missing data. The effect of imbalances between key resident characteristics on the intervention effect will be examined as sensitivity analyses using the change-in-effect method.

For H1, an exploratory analysis will examine antimicrobial courses prescribed for any reason (i.e., not limited to antimicrobials prescribed for suspected UTIs or LRIs). We will compare the number of antimicrobial courses/person-years between the intervention and control arms.

For H1 and H2, exploratory analyses will examine UTIs and LRIs separately.

For H3a, a sensitivity analysis will be conducted to examine if the potential competing risk of death impacts the estimates of cumulative incidence using the Fine-Gray regression model.

For H3b, in addition to examining the combination of all burdensome procedures, each type of burdensome procedure (bladder catheterizations, blood draws, chest x-rays, and hospital transfers) will be examined separately, using a similar analytic approach, as exploratory analyses.

### Appendix A: Tables and Figures

Specifications for planned tables and figures are provided below. Cosmetic changes in style and formatting may be made as needed for presentation and publication requirements.

### A.1 Recruitment and Participant Status

Table A.1.1. Overall Overview of Resident Enrollment over Time\*

[figure not shown]
[figure not shown]

Table A.1.2. Event Completion for All Participants\*

Study Event	Residents
Baseline	
Q1	
Q2	
Q3	
Q4	
Death	

### A.2 Resident Demographics and Baseline Characteristics

Table A.2.1. Demographics and Baseline Characteristics of Residents Overall and by Group

	Total in Study	Group 1	Group 2	Non- Participants
Resident				
Age				
Mean (Median)				
Gender				
Male				
Female				
Race				NA
Black				
White				
Other				
Ethnicity				NA
Hispanic				
Non-Hispanic				
Other				
Health status				NA
Cognitive status				NA
Functional status				NA
Advance care				NA
planning				

### A.3 Adverse Events

Table A.3.1. Overall Listing and Summary of Adverse Events\*

Date	Description of Adverse Event	Action Taken	Outcome
Total # of Adverse events			

Table A.3.2. Listing and Summary of Adverse Events by Group\*\*

Numbe r	Dat e	Description of Adverse Event	Action Taken	Group
1				
2				
3				
4				
5				
6				
Total # o Adverse events				
Total Withdrav from stu				

### A.4 Protocol Deviations and Unanticipated Problems

Table A.4.1. Overall Listing and Summary of Protocol Deviations\*

Number	Date	Protocol Deviation
1		
2		
3		
4		
5		
6		
Total # of Deviations		
Participants Enrolled		
Deviations per Participant		

Table A.4.2. Listing and Summary of Protocol Deviations by Group\*\*

Numb er	Date	Protocol Deviation	Group
1			
2			
3			
4			
5			
6			
Total # of Deviations			

Numb			
er	Date	Protocol Deviation	Group
Participants			
Enrolled			
Deviations per			
Participant .			

Table A.4.3. Overall Listing and Summary of Unanticipated Problems\*

Number	Date	Unanticipated Problem
1		
2		
3		
4		
5		
6		
Total # of Problems		
Participants Enrolled		
Problems per Participant		

Table A.4.4. Listing and Summary of Unanticipated Problems by Group\*\*

Numb er	Date	Unanticipated Problem	Group
1			
2			
3			
4			
5			
6			
Total # of			
Problems			
Participants			
Enrolled			

Nur	mb			
er		Date	Unanticipated Problem	Group
Problems per		is per		
Participant		ant
